6.3. Visit 3 / Enrollment and Implantation (Day 1)

Subjects must be fasted for this visit. Depending on the location of the surgical center, some of these assessments may be performed up to two (2) days prior to implantation day to accommodate logistical considerations. At this visit, the following procedures will be completed:

- Obtain weight and vitals.
- Ensure eligibility criteria continue to be met.
- Perform an abbreviated PE.
- Obtain all laboratory samples per the Schedule of Assessments.
- Perform urine pregnancy test. Results must be available before the implant procedure commences.
- Assess AEs and Concomitant Medications.
- Cohort 2 only:
 - Perform urine drug screen prior to implant procedure.
 - Collect and review CGM, SMBG, and diary data and verify that subject has demonstrated compliance with diary entries. Dispense additional supplies.
- Review Lifestyle Guidelines
 - Review dietary restrictions, physical activity, alcohol/tobacco/caffeine and other guidelines as described under Section 5.4.5.
 - Assess the subject's knowledge of the correct use of contraceptive method, confirm the current contraception method, and the subject's continued correct usage.
- Prepare subject for implantation.
- Implant VC-01 units.

- Obtain video and/or photos of the implantation procedure if requested by the Sponsor (see Section 7.7).
- Dress the subject with the appropriate post-operative garments.
- Assess subject for AEs during post-op period through discharge.
- Subjects may be in post-op up to 4 hours but can be discharged sooner at the discretion of the Surgeon.
- Remind subject of post-op instructions and to limit significant physical activity to ensure optimal healing at implantation sites.

6.4. Visit 4 (Day 2)

There is a +1-day window for this visit. However, if the procedure is performed on a Friday, Visit 4 can be conducted on the following Monday. Subjects do *not* need to fast for this visit. The following procedures will be completed:

- Obtain weight and vitals.
- Perform a targeted PE focusing on the implantation site(s).
- Assess AEs and concomitant medications.
- Cohort 2 only:
 - Collect and review CGM, SMBG, and diary data and verify that subject has demonstrated compliance with diary entries. Dispense additional supplies.
- Review Lifestyle Guidelines
 - Review dietary restrictions, physical activity, alcohol/tobacco/caffeine and other guidelines as described under Section 5.4.5.
 - Assess the subject's knowledge of the correct use of contraceptive method, confirm the current contraception method, and the subject's continued correct usage.

Activities noted below to be performed only if an explant is planned for this visit:

- If unable to locate a unit via palpation, perform an ultrasound to locate the unit(s) planned for explantation (up to 3 days prior).
- Explant unit(s).
- Obtain video and/or photos of the explantation procedure (if requested by Sponsor).
- Dress the subject with the appropriate post-operative garments, if applicable.
- Subjects may be in post-op up to 4 hours but can be discharged sooner at the discretion of the Surgeon.
- Remind subject of post-op instructions and to limit significant physical activity to ensure optimal healing at implantation sites.

6.5. Visit 5 (Week 2)

There is a ± 2 -day window for this visit. Subjects must be fasted for this visit. The following procedures will be completed:

- Obtain weight and vitals.
- Perform an abbreviated PE.
- Obtain laboratory samples per the Schedule of Assessments.
- Assess AEs and concomitant medications.
- Cohort 2 only:
 - Collect and review CGM, SMBG, and diary data and verify that subject has demonstrated compliance with diary entries. Dispense additional supplies.
- Review Lifestyle Guidelines
 - Review dietary restrictions, physical activity, alcohol/tobacco/caffeine and other guidelines as described under Section 5.4.5.
 - Assess the subject's knowledge of the correct use of contraceptive method, confirm the current contraception method, and the subject's continued correct usage.

Activities noted below to be performed only if an explant is planned for this visit:

- If unable to locate a unit via palpation, perform an ultrasound to locate the unit(s) planned for explantation (up to 3 days prior).
- Explant unit(s).
- Obtain video and/or photos of the explantation procedure (if requested by Sponsor).
- Dress the subject with the appropriate post-operative garments, if applicable.
- Subjects may be in post-op up to 4 hours but can be discharged sooner at the discretion of the Surgeon.
- Remind subject of post-op instructions and to limit significant physical activity to ensure optimal healing at implantation sites.

6.6. Visit 6 (Week 4)

There is a ± 3 -day window for this visit. Subjects must be fasted for this visit. The following procedures will be completed:

- Obtain weight and vitals.
- Perform an abbreviated PE.
- Obtain laboratory samples per the Schedule of Assessments.

- Assess AEs and concomitant medications.
- Cohort 2 only:
 - Collect and review CGM, SMBG, and diary data and verify that subject has demonstrated compliance with diary entries. Dispense additional supplies.
- Review Lifestyle Guidelines
 - Review dietary restrictions, physical activity, alcohol/tobacco/caffeine and other guidelines as described under Section 5.4.5.
 - Assess the subject's knowledge of the correct use of contraceptive method, confirm the current contraception method, and the subject's continued correct usage.

Activities noted below to be performed only if an explant is planned for this visit:

- If unable to locate a unit via palpation, perform an ultrasound to locate the unit(s) planned for explantation (up to 3 days prior).
- Explant unit(s).
- Obtain video and/or photos of the explantation procedure (if requested by Sponsor).
- Dress the subject with the appropriate post-operative garments, if applicable.
- Subjects may be in post-op up to 4 hours but can be discharged sooner at the discretion of the Surgeon.
- Remind subject of post-op instructions and to limit significant physical activity to ensure optimal healing at implantation sites.

6.7. Visit 7 (Week 8)

There is a ± 7 -day window for this visit. Subjects must be fasted for this visit. The following procedures will be completed:

- Obtain weight and vitals.
- Perform an abbreviated PE.
- Obtain laboratory samples per the Schedule of Assessments.
- Assess AEs and concomitant medications.
- Cohort 2 only:
 - Collect and review CGM, SMBG, and diary data and verify that subject has demonstrated compliance with diary entries. Dispense additional supplies.
 - Perform 2-hr MMTT.
 - Ultrasensitive C-peptide samples obtained in conjunction with 2-hr MMTT prestimulation (time = 0) and post-stimulation at the 90-minute (+/- 10 minutes) timepoint.
- Review Lifestyle Guidelines

- Review dietary restrictions, physical activity, alcohol/tobacco/caffeine and other guidelines as described under Section 5.4.5.
- Assess the subject's knowledge of the correct use of contraceptive method, confirm the current contraception method, and the subject's continued correct usage.
- Perform the *safety* ultrasound assessment of all remaining implanted sentinels.

Activities noted below to be performed only if an explant is planned for this visit:

- If unable to locate a unit via palpation, perform an ultrasound to locate the unit(s) planned for explantation (up to 3 days prior).
- Explant unit(s).
- Obtain video and/or photos of the explantation procedure (if requested by Sponsor).
- Dress the subject with the appropriate post-operative garments, if applicable.
- Subjects may be in post-op up to 4 hours but can be discharged sooner at the discretion of the Surgeon.
- Remind subject of post-op instructions and to limit significant physical activity to ensure optimal healing at implantation sites.

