| Physical Exam (Abbreviated) | | | X | | X | X | X | X | X | X | | X | | |
| Physical Exam (Targeted) | | | | X | | | | | | | | | | X |
| Height | X | | | | | | | | | | | | | |
| Weight / Vitals | X | X | X | X | X | X | X | X | X | X | X | X | X | X |
| Review Lifestyle Guidelines | X | X | X | X | X | X | X | X | X | X | X | X | X | |
| Confirm Implant date w/Sponsor | X | | | | | | | | | | | | | |
| Dispense/Review CGM Data | | X | X | X | X | X | X | X | X | X | X | X | X | |
| Dispense/Review Diary Data | | X | X | X | X | X | X | X | X | X | X | X | X | |
| Dispense/Review SMBG Supplies | | X | X | X | X | X | X | X | X | X | X | X | X | |
| Implantation Procedure | | | X | | | | | | | | | | | |
| Post-Implant Education/Therapies | | | X | | | | | | | | | | | |
| Explantation Procedure | | | | | | X | (time- poin | ts as determine | ed by Sponso | or) | | l | X | |
| Ultrasound - Safety | | | | | | | X | | X | | X | | X | |
| Ultrasound - Pre-Explant ^a | | | | | | X (tin | ne- points T | BD based on e | xplant proce | edures) | | | X | |
| Video and Photos ^b | | | X | | | X (addition | al time- poi | nts TBD based | on explant | procedures |) | | X | X |
| AE and Concomitant Medications | | X | X | X | X | X | X | X | X | X | X | X | X | X |
| Distribute Urine Sample Supplies for albumin/creatinine test (for next visit 1st morning void) | X | _ | | | | | | | | X | | X | | |
| ICD for Follow-Up Study | | | | | | | | | | | | | | X |

| | V1 Screen | V2 Screen | V3 ^j Enroll | V4 | V5 | V6 | V7 | V8 | V9 | V10 | V11 | V12 | V13 or ET | V14 Follow- Up |
|--|--------------|----------------|---------------------------|-------|---------|---------|----------|----------|----------|----------|----------|-----------|--------------|-------------------|
| Assessments (Visit Windows) | Wk -5 | Wk -4 | Day 1 | Day 2 | Wk 2 | Wk 4 | Wk 8 | Wk 12 | Wk 16 | Wk 20 | Wk 26 | Wk 39 | Wk 52 | Wk 53 |
| | | | | (+1d) | (+/-2d) | (+/-3d) | (+/- 7d) | (+/- 14d) | (+/- 7d) | (+/- 3d) |
| Central Laboratory Tests or Study-Pr | ovided Test | ing Kits | | | | | l . | | | | | | | |
| Drug Screen ^d | X | | X | | | | | | | | | | | |
| HBsAg, HCV, HIV | X | | | | | | | | | | | | | |
| Hematology & Chemistry | X | X | X | | X | X | X | X | X | X | X | X | X | |
| eGFR | X | | | | | | | | | | | | | |
| HbA1c | X | | X | | | | | | X | | X | | X | |
| FSHe | X | | | | | | | | | | | | | |
| Urine Pregnancy Test ^f | X | | X | | | | | | | | | | X | |

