The DSMB will not meet regularly during Cohort 1 unless the Sponsor seeks an independent DSMB review based on Sponsor or Ethics Committee (EC) recommendations for managing AEs.

3.2. Cohort 2

Upon confirmation of histological response in Cohort 1 subjects, demonstrating engraftment and the potential for clinical efficacy at a higher (therapeutic) dose, enrollment in the Efficacy Cohort 2 will be initiated.

In Cohort 2, the Screening Period for each subject is expected to be approximately five (5) weeks in duration and comprised of two (2) study visits. Subjects qualifying for entry into Cohort 2 and who subsequently are implanted with VC-01 sentinel units and/or dose-finding units (VC-01-DF) may complete an additional 12 visits over a period of approximately one (1) year. It is expected that a subject who completes the planned entire duration of the trial will therefore have a total of 14 study visits spanning approximately 13 ½ months (including Screening, Treatment Period, and final Follow-up Visit). If the Sponsor has planned/scheduled an earlier explant (for non-safety reasons), this subject will also be considered as completing the study early (ET) with fewer study visits, as applicable.

Up to 40 subjects will receive subcutaneous implantation of:

- O Up to nine (9) VC-01-DF units, or;
- Up to 12 units total. Of the 12 units, no more than nine (9) will be dose-finding (VC-01-DF) and the remainder may be sentinel units. For example, if seven (7) VC-01-DF units are implanted in a subject, up to five (5) sentinels may be implanted.

The number of VC-01-DF units to be implanted in Cohort 2 subjects will be a data-driven decision and may vary between subjects. The Sponsor will review available C-peptide results from ongoing subjects to determine the optimal number of VC-01-DF units to implant in subsequent subjects. The Sponsor generally intends to implant the least number of VC-01-DF units required to provide the intended therapeutic benefit. Pre-clinical data suggest VC-01-DF units may provide enough therapeutic benefit to allow a subject to discontinue exogenous insulin. However, if VC-01 does not function as robustly in humans as observed in pre-clinical models, then the number of VC-01-DF units required may be

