5.1.4. Dosage and Administration

All properly consented subjects will receive a unique, study subject ID number. Those subjects meeting eligibility criteria are enrolled at Visit 3/Day 1 and implanted with VC-01. As this is an open-label study, the subject, Sponsor, and Investigator are not blinded and will know how many and which types of VC-01 are implanted, depending on the Cohort.

In Cohort 1, each subject can be implanted with up to ten (10) sentinel units.

In Cohort 2, each subject can be implanted with up to 12 VC-01 units total. Of the 12 units, no more than nine (9) will be dose-finding (VC-01-DF) and the remainder may be sentinel units. For example, if the maximum of nine (9) VC-01-DF units are scheduled for implant, only three (3) sentinel units may be included in the implantation plan. Or if only seven (7) VC-01-DF units are planned, then five (5) sentinel units can be implanted.

The administration of the investigational product is performed via implantation on Visit 3 (Day 1). The preparation and implantation procedures involve step-by-step instructions which are detailed in **Section 7.2** and the Instructions for Use (IFU). Site personnel will be trained to ensure compliance with the product handling and implantation procedures.

Due to the nature of the product under investigation, "dose" adjustments (e.g., an increase or decrease) of the implanted VC-01 are not permitted. However, in Cohort 2, at the discretion of the Sponsor and after consultation with the Investigator, explantation of up to two (2) VC-01-DF units is allowed at any time post-implant for a subject without needing to withdraw the subject from the study. Depending on the experience of each subject, the Investigator or subject may elect to have the subject withdrawn from the study and have the VC-01-DF units and all remaining sentinels explanted.

Since VC-01 is implanted into each subject, assessment of subject compliance with the investigational product does not apply. If, however, the expected number of units is not implanted into a subject, this needs to be recorded in the subject's source documentation.

5.1.4.1 Cohort 1

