6. STUDY SCHEDULE

The visit schedule for study subjects is outlined in the Schedule of Assessments, **Table 1** (Cohort 1) and **Table 2** (Cohort 2). If needed, procedures may occur separate days, though they should be done within the defined protocol window. Some assessments are only required for Cohort 2 and are indicated as such. With documented sponsor permission, on a case-by-case basis, certain protocol-required assessments may be performed remotely.

To minimize variability in data, sites should attempt to schedule visits on the same day of the week and same time of day for a subject throughout the trial. When multiple procedures occur at a visit, the following order of procedures should be adhered to as much as possible:

- 1. 12-lead ECG (performed after the subject has rested for at least 10 minutes in a supine position)
- 2. Vital signs (sitting blood pressure, pulse, and temperature)
- 3. Blood and urine samples
- 4. Cohort 2 Only: Simplified Oral Glucose Challenge Test (SOGCT) (Visit 1 only) or Mixed Meal Tolerance Test (MMTT) (Visits 2 13). For visits requiring both an MMTT and an explant procedure, the site may perform the MMTT within five (5) days prior to the explant procedure.
- 5. Ultrasound Monitoring

- 6. Implant or explant procedures
- 7. Other procedures: May be obtained in any order either prior to blood samples or after, but not sooner than ECG or vitals.

Caffeine and nicotine products are prohibited for at least 30 minutes prior to ECG and vital sign determinations.

Ultrasounds performed for the purpose of locating the implanted units prior to an explantation procedure may be done up to 3 days prior to the explantation.

6.1. Screening Visit 1 (Cohort 1: Week -2 to Week -1; Cohort 2: Week -5 to Week -4)

The Screening Period is comprised of two visits: Visit 1 and Visit 2. For Cohort 1, the Screening Period can be performed over approximately two (2) weeks, whereas Cohort 2 can be over approximately five (5) weeks. It is permissible for Screening Visit 1 procedures to occur over multiple days. Subjects must be fasted for this visit. The following procedures will be completed:

- Obtain informed consent.
 - *Note*: It is acceptable for consent to be obtained prior to the Screening Visit 1.
- Obtain a 12-lead ECG (performed after the subject has rested for at least 10 minutes in a supine position)
- Obtain weight and vitals.
- Measure height

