7.9. Ultrasound Monitoring

Ultrasound monitoring will be performed by trained personnel either read locally at the clinical site or by a central imaging center. For consistency of results, it is recommended the same technician at the site perform all ultrasound evaluations on a subject and the same machine is used on a subject throughout the trial. Ultrasound monitoring in this study serves two purposes:

- Safety evaluations to monitor graft performance; and
- To pre-identify the anatomical location of implanted units prior to an explantation procedure.

These purposes are discussed in more detail below.

The safety ultrasound images will be captured, transmitted, and analyzed at Visit 7 (Week 8), Visit 9 (Week 16), Visit 11 (Week 26), and Visit 13 (Week 52 - Cohort 2 only) or early completion/termination.

• **Location Ultrasounds**: These ultrasound evaluations will be performed within three (3) days prior to all scheduled explantation for surgical planning purposes. The technician locates the unit(s) planned for explant and then outlines its location with surgical marker. This allows the Surgeon to minimize tissue trauma and reduces the likelihood of disturbing adjacent implants.

If a safety ultrasound procedure and anatomical location ultrasound are required at the same visit, both can be completed within the same imaging session. Conversely, there may be visits where safety ultrasounds are required but do not correspond to a visit requiring an explant procedure, and therefore, location ultrasounds (surgical marking) are not required (and vice versa). Refer to the applicable Schedule of Assessments for the complete listing of when any ultrasound imaging may be required.

Clinical studies conducted by ViaCyte investigating this product indicate the established ultrasound imaging procedure is successful at imaging implanted units and is appropriate for the purposes identified above. If modifications to the ultrasound procedure are considered necessary based on data collected over the course of the trial, sites will be notified.

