10.4.4.2.3. Cohort 2 Secondary Exploratory Analyses

summarized by treatment group and time point. The Sponsor may explant sentinel units beginning at the Week 4 time point. However, as data is collected in the trial, it will inform that evaluation at additional time points may be required.

Histology results will be summarized by explant time point, anatomical location, and treatment group for Cohort 2. Additional details will be outlined in the SAP.

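### Visit sections 6.7 (Week 8) and 6.9 (Week 16) cover both cohorts but word the safety ultrasound for sentinels only, leaving out the VC-01-DF units of Cohort 2

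*Protocol*

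**What the plan says.** Protocol 6.7 (Visit 7, Week 8) and 6.9 (Visit 9, Week 16) are single sections for both cohorts. Each has a block marked for Cohort 2 only, which holds the diary and glucose review, the MMTT and the ultrasensitive C-peptide samples. Outside that block, as an item for everyone, each section asks for the safety "ultrasound assessment of all remaining implanted sentinels".

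Other parts of the plan describe the Cohort 2 scan more broadly:

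- **Table 2 (Cohort 2 schedule).** The row "Ultrasound - Safety" is marked at Visits 7, 9, 11 and 13, with no limit to sentinels.
- **Section 7.9.** It lists Weeks 8, 16, 26 and 52 and marks only Week 52 as specific to Cohort 2. For timing it tells sites: "Refer to the applicable Schedule of Assessments for the complete listing of when any ultrasound imaging may be required".
- **Sections 6.11.2 and 6.13 (Cohort 2 only, Weeks 26 and 52).** The scan covers every unit still implanted.
- **Section 6.11.1 (Cohort 1 only, Week 26).** The sentinel wording appears here and is correct, because Cohort 1 receives only sentinels.
- **Section 1.4.2.1.** Ultrasound monitoring over the course of the trial is described for implanted units in general.
- **SAP 4.2 and 7.3.7.2.** Off-target growth in Cohort 2 is assessed on implanted VC-01 units, with a lumen thickness above 1 mm on ultrasound as one criterion.

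On what Cohort 2 subjects carry, section 3.2 allows "Up to nine (9) VC-01-DF units, or" a mix of up to 12 units. Section 10.4.4.2.3 adds: "The Sponsor may explant sentinel units beginning at the Week 4 time point".

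**The concern.** The visit sections are the instructions a site works from on the day. At Weeks 8 and 16 they name only the sentinels, although the larger VC-01-DF units carry the therapeutic dose in Cohort 2. The mismatch is plainest for a Cohort 2 subject with no sentinel in place, either because none was implanted or because all had been explanted by then. Table 2 requires a scan at that visit, and the visit text gives nothing to scan.

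This is a safety check. Section 1.2 presents lumen expansion on ultrasound as a sign of possible unsafe off-target growth, and example 4a under the stopping rules in section 8.6 describes such growth as noted on ultrasound and confirmed by a pathologist. A site could follow 6.7 and 6.9 to the letter and leave the VC-01-DF units without a planned safety scan until Week 26.

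**Working it through.** The plan gives no figure to reproduce. The check compares the scope of the scan visit by visit for Cohort 2, then works out what a literal reading would cost.

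**Scope by visit (Cohort 2)**

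| Visit | Scheduled in Table 2 and 7.9 | Units named in the visit section |
|---|---|---|
| Week 8 | Yes | Sentinels only (6.7) |
| Week 16 | Yes | Sentinels only (6.9) |
| Week 26 | Yes | All units (6.11.2) |
| Week 52 | Yes | All VC-01 units (6.13) |

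Four safety scans are planned. The visit text covers VC-01-DF units at two of them.

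**Delay to the first planned scan of VC-01-DF units, literal reading**

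Inputs: target days from SAP 7.2.2 (Week 8 = Day 57, Week 16 = Day 113, Week 26 = Day 183) and the protocol's ±7-day windows.

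- Growth already visible at Week 8: 183 − 57 = 126 days = 18 weeks. Shortest: 176 − 64 = 112 days = 16 weeks. Longest: 190 − 50 = 140 days = 20 weeks.
- Growth first visible at Week 16: 183 − 113 = 70 days = 10 weeks. Shortest: 176 − 120 = 56 days = 8 weeks. Longest: 190 − 106 = 84 days = 12 weeks.
- Growth that becomes visible only after Week 16: no delay.
- Site applies Table 2 to all units: no delay in any case, and four scans.

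**Share of units covered at Weeks 8 and 16, literal reading**

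Unit mixes from 3.2 and 5.1.4, before any explant. With nine VC-01-DF units, 5.1.4 says "only three (3) sentinel units may be included in the implantation plan".

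- Nine VC-01-DF and no sentinels: 0 of 9.
- Nine VC-01-DF and three sentinels: 3/12 = 25%.
- Seven VC-01-DF and five sentinels: 5/12 = 42%.

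For the two mixes with sentinels these shares are upper limits, because they fall as sentinels are explanted.

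**The case against.** The strongest reply is that this is a drafting slip whose effect depends on text that cannot be seen. Section 7.9 announces a description of both ultrasound purposes, but the public version shows only the one for locating units. The safety description may well say which units are scanned. Table 2 and 7.9 fix when scans happen and not which units are imaged, so for a subject with sentinels in place, scanning the sentinels breaks neither. Section 6 also sends sites to the schedule ("The visit schedule for study subjects is outlined in the Schedule of Assessments"), and many would image every unit.

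There are other safeguards. Section 6.15 allows repeat or follow-up ultrasounds at unplanned visits. Section 7.10.2 expects sentinels to behave much like VC-01-DF units. Histology of explants also feeds the off-target-growth count. Item 4a in section 8.6 is an example under a broader rule, so the wording disables no stopping rule. The delay figures assume that growth exists in VC-01-DF units and is visible early, while sections 1.4.2 and 1.4.2.1 report none in the clinic to date.

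Most of this stands, and it limits the size of the point. It does not remove the mismatch. If the unseen text in 7.9 says all units, 6.7 and 6.9 disagree with it. If it says sentinels only, it disagrees with 6.11.2 and 6.13. The pointer to the schedule does not settle scope either, because Table 2 does not say which units to scan. In the visible text, 6.7 and 6.9 are the only visit-level instructions on that question at Weeks 8 and 16.

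**Conclusion.** The concern holds. It is a mismatch of scope between the shared visit sections and the rest of the plan, and not a contradiction of an explicit all-units statement at Weeks 8 and 16. The wording in 6.11.2, 6.13, section 1.4.2.1 and the SAP makes the intention to scan all units fairly clear, and Cohort 1 wording carried forward is the likely cause.

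The consequence runs from nothing, if sites apply Table 2 to every unit, to the loss of two of the four planned safety scans of VC-01-DF units and a first scan 18 weeks late. The upper end assumes that the site follows the visit text alone and that no unplanned scan is done. The delay matters clinically only if growth in a VC-01-DF unit would have been visible at Week 8 or 16. The primary analysis is unaffected, and no bias in the reported incidence of off-target growth is shown. The correction should be made because this is an operative safety instruction and the change is very small.

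**What to change.** In 6.7 and 6.9, replace the reference to sentinels with *all remaining implanted VC-01 units (sentinel and VC-01-DF)*, in line with 6.11.2 and 6.13.

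Optionally, make the same correction in 13.6.1, where the paragraph on subjects lost to contact speaks of removing the sentinels. This matters less, because that section already requires all remaining VC-01 units to be explanted on withdrawal.

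The cost is one phrase in two sections, or three with the optional edit. No visit is added, since Table 2 already schedules both scans. The only added work is imaging more units at scans already planned. The SAP needs no change.
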